
To evaluate the pharmacodynamics (PD) of single ascending oral doses of kratom in healthy nondependent recreational polydrug users with opioid experience.
	
The PD endpoint of this study is the maximum (peak) effect (<math>E_{max}</math>) over 24 hours for Drug Liking (“at this moment”), assessed on a bipolar (0 to 100 points) visual analog scale (VAS).
 
Key secondary PD endpoints are:
 
 
• Overall Drug Liking VAS (<math>E_{max}</math>)
 
• Take Drug Again VAS (<math>E_{max}</math>)
 
• High VAS (<math>E_{max}</math>)
 
 
Non-key secondary PD endpoints are:
 
 
• Balance of Effects 
 
○ Drug Liking VAS (minimum effect [<math>E_{min}</math>], time of maximum effect [<math>TE_{max}</math>], time of minimum effect [<math>TE_{min}</math>], and time-averaged area under the effect-time curve [TA_AUE])
 
 
 
• Positive Effects 
 
○ Good Effects VAS (<math>E_{max}</math>, <math>TE_{max}</math>, and TA_AUE)
 
○ High VAS (<math>E_{max}</math>, <math>TE_{max}</math>, and TA_AUE)
 
 
 
• Negative Effects 
 
○ Bad Effects VAS (<math>E_{max}</math>, <math>TE_{max}</math>, and TA_AUE)
 
 
 
• Other Subjective Effects 
 
○ Any Effects VAS (<math>E_{max}</math>, <math>TE_{max}</math>, and TA_AUE)
 
○ Feeling Drunk VAS (<math>E_{max}</math>, <math>TE_{max}</math>, and TA_AUE)
 
○ Drowsiness/Alertness VAS (<math>E_{max}</math>, <math>TE_{max}</math>, <math>E_{min}</math>, <math>TE_{min}</math>, and area over and under the effect-time curve [TA_AOE, TA_AUE])
 
○ Relaxation/Agitation (<math>E_{max}</math>, <math>TE_{max}</math>, <math>E_{min}</math>, <math>TE_{min}</math>, and TA_AOE, TA_AUE)
 
○ ARCI MBG Scale (<math>E_{max}</math>, <math>TE_{max}</math>, and TA_AUE)
 
○ ARCI A Scale (<math>E_{max}</math>, <math>TE_{max}</math>, and TA_AUE)
 
○ ARCI BG Scale (<math>E_{max}</math>, <math>TE_{max}</math>, and TA_AUE)
 
○ ARCI PCAG Scale (<math>E_{max}</math>, <math>TE_{max}</math>, and TA_AUE)
 
 
 

---	---

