## 9 PHARMACODYNAMIC ANALYSIS

Unless otherwise specified, all available PD data and analysis results will be presented for the Completer population.

The PD measures at each time point will be summarized by treatment using descriptive statistics and presented graphically. Derived endpoints will be summarized by treatment and paired difference using descriptive statistics.

Descriptive statistics will include n, mean, standard error (SE), minimum, first quartile (Q1), median, third quartile (Q3) and maximum for all PD values and endpoints other than  $TE_{max}$  and  $TE_{min}$ . For  $TE_{max}$  and  $TE_{min}$ , minimum, Q1, median, Q3 and maximum will be presented.

Derivations for PD endpoints will be calculated as described below:

PD Endpoints	Definition
$E_{min}$	Minimum observed post-dose effect
$E_{max}$	Maximum observed post-dose effect
$TE_{min}$	Time of minimum observed post-dose effect
$TE_{max}$	Time of maximum observed post-dose effect
TA_AUE 	Time-averaged area under the effect-time curve (pre-dose - post-dose)
TA_AOE 	Time-averaged area over the effect-time curve (pre-dose - post-dose)

For time-averaged area over the effect-time-curve and area under the effect-time-curve (TA-AUE and TA\_AOE), will be calculated as the area over(or under) the curve relative to the baseline value divided by the time from time 0 to the X hour time point. TA\_AOE will be calculated using the linear trapezoidal rule applied to non-missing data. TA\_AOE will not be calculated if the first or last scheduled time point are missing. Assessments performed outside the assessment windows may be excluded from by-time point summary statistics; this will be determined prior to unblinding.

Derived Variable	Variables Used	Calculation	Comment

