TA_AUE and TA_AOE	PD effect score $E_i$ at actual elapsed times $t_i$ over one inter-dosing interval.	$AUE_i = (t_i - t_{i-1}) \frac{(E_i + E_{i-1})}{2}$ 
then
 $AUE = \sum_{i=1}^n AUE_i$ 
summation over all time intervals from time 0 (or the first time point if the PD measure is not collected predose) to the X-hour (ie, last) time point.
 
TA_AUE is calculated as the AUE divided by the time from time 0 (or the first time point if the PD measure is not collected predose) to the X-hour time point.
 
TA_AOE will be calculated using the same procedure and TA_AUE with the exception that increases compared to baseline are expected so areas are expected to fall over baseline instead if below baseline.
	Trapezoidal rule used to the 2 consecutive non-missing data points Missing data are ignored. The actual elapsed time $t_0$ for the predose value is set to 0.

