**Table 9-2. Acceptable Windows for Timed Pupillometry Measurements**

Elapsed Time	Accepted Window
Predose (Day 1)	Within 60 minutes prior to study drug administration
Postdose	Within 5 minutes following collection of PK blood sample

The following Pupillometry endpoints will be derived.

- Maximum pupil constriction as assessed by the difference between initial pupil diameter and minimum pupil diameter (MPC)
- Time to maximum pupil constriction
- Pupillometry area over the curve (time-averaged pupillometry area over the effect curve relative to baseline [TA\_PAOC]). TA\_PAOC will be calculated as the area over the effect curve relative to baseline divided by the time from time 0 to the last time point post-dose or specific time point.

Pupil diameter will be summarized by treatment, visit and time point using descriptive statistics. Derived endpoints will also be summarized by treatment using descriptive statistics.

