**Table 9-3. Subjective Measures Schedule**

Category	Evaluations	Timepoints
Drug-specific VAS	Drug Liking, Good Drug Effects, Bad Drug Effects, and Any Drug Effects	0.25, 0.5, 1, 1.5, 2, 2.5, 3, 4, 6, 8, 10, 12, and 24 hours postdose
	Overall Drug Liking and Take Drug Again	12 and 24 hours postdose
Other VAS	High, Feeling Drunk, Relaxation/Agitation, Drowsiness/Alertness, and Bowdle VAS	Predose and 0.25, 0.5, 1, 1.5, 2, 2.5, 3, 4, 6, 8, 10, 12, and 24 hours postdose
	Drug Similarity	12 hour postdose
ARCI Scales	MBG, A, BG, PCAG, and LSD	Predose and 0.25, 0.5, 1, 1.5, 2, 2.5, 3, 4, 6, 8, 10, 12, and 24 hours postdose

Abbreviations: A = amphetamine; BG = Benzedrine Group; LSD = Lysergic Acid Diethylamide; MBG = Morphine-Benedrine Group; PCAG = Pentobarbital–Chlorpromazine–Alcohol Group; VAS = visual analog scale.

Windows for timed subjective measurements are presented in [Table 9-4](#).

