### 9.3 Analysis of Pharmacodynamics Measures

The primary PD endpoint of this study is the maximum (peak) effect (Emax) over 24 hours for Drug Liking (“at this moment”), assessed on a bipolar (0 to 100 points) visual analog scale (VAS). This endpoint will be summarized with descriptive statistics. Placebo will be pooled across all cohorts.

$E_{max}$  as well as  $T_{max}$  and TA\_AUE of key secondary PD endpoints, Overall Drug Liking, Take Drug Again, and High VAS will be summarized similarly by treatment for the Completer population using descriptive statistics. All PD measures at each time point will be summarized by treatment using descriptive statistics and presented graphically. Derived endpoints will be summarized by treatment and paired difference using descriptive statistics.

A mixed-effects model will be used to compare PD endpoints between Kratom dose levels and placebo for all primary and secondary PD endpoints other than the 12-hour postdose results from Drug Similarity VAS and  $TE_{max}$  and  $TE_{min}$  endpoints. The model will include dose level as a fixed effect and the baseline score as a covariate [where applicable]. P-values for key components of variance, least-square means (LSmeans), and 95% CI for contrasts will be output for each pairwise comparison for Kratom dose levels versus placebo.

For each PD endpoint, the following comparison will be made:

- Kratom 1 g vs. Placebo
- Kratom 2 g vs. Placebo
- Kratom 4 g vs. Placebo
- Kratom 6 g vs. Placebo
- Kratom 8 g vs. Placebo

The Hodges-Lehmann estimate of the location shift, the asymptotic confidence limits, and the asymptotic standard error estimate will be used to estimate the 95% CIs of  $TE_{max}$  and  $TE_{min}$  secondary endpoints between the Kratom dose levels and placebo. The asymptotic standard error estimate is based on the length of the CIs. Rank sums and p-values from the Wilcoxon Rank Sum test will also be output.

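### SAP section 9 gives incompatible derivations for TA_AUE and TA_AOE; taken literally, its only formula returns one number for both on the two scales that report both

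*SAP*

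**What the plan says.** SAP section 9 describes the two areas in two places.

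- **Footnote 1 to the endpoint definitions** covers both measures and takes the "area over(or under) the curve relative to the baseline value divided by the time from time 0 to the X hour time point".
- **The derived-variable table** gives the only formula: the sum of (t_i − t_{i−1})(E_i + E_{i−1})/2 on the score E itself. For the divisor it uses the "AUE divided by the time from time 0 (or the first time point if the PD measure is not collected predose"). For the second measure it says "TA_AOE will be calculated using the same procedure and TA_AUE with the exception that increases compared to baseline are expected", and places the area on the upper side of baseline.

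Elsewhere in the SAP:

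- **Section 9.1 Pupillometry** has an area over the curve for pupil constriction, which is a decrease. TA_PAOC "will be calculated as the area over the effect curve relative to baseline divided by the time from time 0" to the last or a specified time point.
- **Table 2-1** lists "area over and under the effect-time curve [TA_AOE, TA_AUE"] for Drowsiness/Alertness and the same pair for Relaxation/Agitation. No other scale has both. For Overall Drug Liking and Take Drug Again it lists Emax only.
- **Tables 9-3 and 9-5** show no predose score for Drug Liking, Good, Bad and Any Effects (first rating at 0.25 h), nor for Overall Drug Liking and Take Drug Again (rated at 12 h and 24 h only).
- **Section 9.3** fits a model with dose level and, where applicable, the baseline score as covariate. It also says that Emax, the time of maximum and TA_AUE "of key secondary PD endpoints, Overall Drug Liking, Take Drug Again, and High VAS will be summarized similarly by treatment".

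**The concern.** Footnote 1 and the formula are different calculations, and the sentence that should separate TA_AOE from TA_AUE states an expectation about direction without giving a different computation. That direction is also opposite to the one in SAP 9.1. Two programmers could each cite the SAP and deliver different numbers under the same label.

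This matters most on Drowsiness/Alertness and Relaxation/Agitation, where two areas are listed in order to separate two directions of effect. Protocol 1.3 describes stimulant-like effects at lower doses and sedation at higher ones, so direction on these scales is something the study wants to see. SAP section 5 treats analyses performed after database lock or unblinding as post hoc, so a choice made then would no longer count as prespecified.

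The divisor is a secondary matter: footnote 1 always starts the clock at time 0, whereas the table starts it at the first rating when there is no predose score.

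**Working it through.** The documents give no numerical TA_AUE or TA_AOE, so there is no figure to reproduce. All scores below are assumptions. The time grid is SAP Table 9-3: predose (0), 0.25, 0.5, 1, 1.5, 2, 2.5, 3, 4, 6, 8, 10, 12 and 24 h.

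**1. The two bipolar scales, predose 50.**

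- Profile A falls linearly to 20 at 3 h and returns linearly to 50 at 10 h. Area below baseline = 0.5 × 10 × 30 = 150; 150/24 = 6.25. Raw time-average = 50 − 6.25 = 43.75.
- Profile B is flat at 50.
- Profile C rises to 70 at 1 h, is 50 at 2 h, 40 at 4 h and 50 from 6 h. Above: 0.5 × 2 × 20 = 20. Below: 0.5 × 4 × 10 = 20. Each is 20/24 = 0.83.

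| Profile | Literal formula, TA_AUE and TA_AOE alike | Above predose | Below predose | Net |
|---|---|---|---|---|
| A | 43.75 | 0 | 6.25 | −6.25 |
| B | 50.00 | 0 | 0 | 0 |
| C | 50.00 | 0.83 | 0.83 | 0 |

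For profile A with a low point of 40, 30, 20 or 10, the formula gives 47.92, 45.83, 43.75 or 41.67, and the area below baseline is 2.08, 4.17, 6.25 or 8.33.

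For profile A, TA_AOE is therefore 43.75 by the literal formula, 0 if it means area above baseline (the table's sentence), and 6.25 if it means area below baseline (the usage in SAP 9.1).

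**2. What reaches the model.** Net area = raw area − predose, since subtracting a constant baseline b removes 24b/24 = b. With predose as covariate, changing the outcome from raw to net lowers the covariate slope by 1 and leaves every dose-placebo contrast unchanged. On simulated data with the planned layout (5 × 2 = 10 pooled placebo, 5 doses × 6), the contrasts agreed to rounding error. One-sided areas are not linear in the scores, so this equivalence does not extend to them.

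**3. Other predose scales.** For High, Feeling Drunk and the five ARCI scales, footnote and formula differ by the predose score. By step 2, descriptive summaries change and adjusted contrasts do not.

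**4. Divisor.**

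- Ratings from 0.25 h (Drug Liking, Good, Bad, Any Effects): 23.75/24 = 0.990. A constant 60 gives area 60 × 23.75 = 1425; 1425/23.75 = 60.00 and 1425/24 = 59.38.
- Ratings at 12 and 24 h only: the table's area is 12 × mean, so its own 12 h divisor returns the mean. For (70, 60), 780/12 = 65. Dividing that same area by 24 h would give 32.5.

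**5. Noise cost of one-sided areas.** Simulation with independent normal error at every time including predose, and no clipping at 0 or 100:

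| Assumed error SD | Mean area on each side, true score flat | Profile A minus flat, area below (true 6.25) |
|---|---|---|
| 2 | about 1.0 | about 5.8 |
| 5 | about 2.6 | about 5.3 |
| 10 | about 5.1 | about 4.7 |

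The net-area difference stays close to −6.25 throughout.

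**The case against.** The best defence is that the SAP can be read coherently. Footnote 1 names areas over and under the curve relative to baseline, and the table's exception also speaks of baseline, so the equation may show only the mechanics of the trapezoid, with the footnote supplying the reference. That has force: a reader might infer that the two endpoints are bound to be reported as one number, and the documents do not support this. Identity is what the formula yields when followed literally. The reading still does not rescue the text, because direction remains contradictory between the table and SAP 9.1.

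The matching pre-dose/post-dose tags on both definition rows should not be counted as a direction error, since they may simply mark the time span.

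A reader might also infer that TA_AUE for Overall Drug Liking and Take Drug Again will be halved, so that a neutral (50, 50) reads 25. That needs footnote 1's divisor joined to the table's area, and neither place gives that combination. The table alone is consistent. Footnote 1 alone cannot be computed without a predose score. Moreover, TA_AUE for these scales appears only in the descriptive sentence of SAP 9.3.

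The defence is also right that profile C needs opposite phases within one subject. No section states such a course; protocol 1.3 contrasts doses, and each subject receives one. With a one-directional effect the raw area keeps its size, as A minus B shows (43.75 − 50.00 = −6.25).

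**Conclusion.** The point holds as a contradiction in the stated derivation. Baseline reference and direction are each given two ways, and the literal formula makes two listed, modelled endpoints identical on Drowsiness/Alertness and Relaxation/Agitation. In the assumed profile A the same label could be reported as 43.75, 0 or 6.25.

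Its reach is limited. In the model only the one-sided split on these two non-key secondary scales depends on the choice, given that predose is the covariate and is also the time-0 value in the area. Safety, PK, Emax and Emin with their times, and TA_PAOC are untouched, and time-point summaries and graphs still show direction. The divisor discrepancy is about 1% on the four drug-specific scales that start at 0.25 h, and a constant divisor does not alter p-values. It should be corrected because the rule as written is wrong and cheap to put right. The profiles and error SDs are assumptions; the identity of the two areas under the literal formula and the divisor ratio are not.

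**What to change.** Before database lock and unblinding, amend SAP section 9:

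1. For Drowsiness/Alertness and Relaxation/Agitation, add the baseline term to the calculation. Define TA_AUE as area above predose and TA_AOE as area below predose, consistent with SAP 9.1, with interpolation where the curve crosses baseline, and replace the reversed sentence. State the downside: one-sided areas are positive under pure noise, and noise shrinks their difference from placebo (about 4.7 against 6.25 at an assumed error SD of 10), so they should be read only against placebo. Reporting the net area beside them is optional.
2. State one baseline reference for High, Feeling Drunk and the five ARCI scales.
3. Copy the no-predose exception into footnote 1: no baseline subtracted, divisor from the first time point.
4. For Overall Drug Liking and Take Drug Again, either apply that rule (12 h divisor, equal to the mean of the two ratings) or delete their TA_AUE from SAP 9.3, since Table 2-1 lists only Emax.
5. Name the form used (one-sided, net or raw) in each table title, because TA_AUE will not have the same form on every scale.

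The cost is SAP wording, one programming specification and table titles. No new data are needed. The price of the one-sided definition is the noise bias in item 1.

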## 9.1 Pupillometry

Pupillometry will be used as an objective physiological PD measure as it is a sensitive measure of central opioid action and appears to be resistant to tolerance development with repeated administration. An electronic pupillometer will be used to measure pupil diameter. For each subject, every effort will be made to use the same eye for all assessments throughout the study. The pupillometry assessments will be completed immediately prior to the administration of all other PD measures. Pupil diameter will be measured as per the timepoints outlined in [Table 9-1](#).

**Table 9-1. Pupillometry Schedule**

Pupillometry - Scheduled Time Points
Day 1: predose and 0.5, 1, 1.5, 2, 2.5, 3, 4, 6, 8, 10, and 12 hours postdose
Day 2: 24 hours postdose

Windows for timed pupillometry measurements are presented in [Table 9-2](#).

**Table 9-2. Acceptable Windows for Timed Pupillometry Measurements**

Elapsed Time	Accepted Window
Predose (Day 1)	Within 60 minutes prior to study drug administration
Postdose	Within 5 minutes following collection of PK blood sample

The following Pupillometry endpoints will be derived.

- Maximum pupil constriction as assessed by the difference between initial pupil diameter and minimum pupil diameter (MPC)
- Time to maximum pupil constriction
- Pupillometry area over the curve (time-averaged pupillometry area over the effect curve relative to baseline [TA\_PAOC]). TA\_PAOC will be calculated as the area over the effect curve relative to baseline divided by the time from time 0 to the last time point post-dose or specific time point.

Pupil diameter will be summarized by treatment, visit and time point using descriptive statistics. Derived endpoints will also be summarized by treatment using descriptive statistics.

## 9.2 Subjective Effects

Subjective measures are detailed in [Table 9-3](#).

**Table 9-3. Subjective Measures Schedule**

Category	Evaluations	Timepoints
Drug-specific VAS	Drug Liking, Good Drug Effects, Bad Drug Effects, and Any Drug Effects	0.25, 0.5, 1, 1.5, 2, 2.5, 3, 4, 6, 8, 10, 12, and 24 hours postdose
	Overall Drug Liking and Take Drug Again	12 and 24 hours postdose
Other VAS	High, Feeling Drunk, Relaxation/Agitation, Drowsiness/Alertness, and Bowdle VAS	Predose and 0.25, 0.5, 1, 1.5, 2, 2.5, 3, 4, 6, 8, 10, 12, and 24 hours postdose
	Drug Similarity	12 hour postdose
ARCI Scales	MBG, A, BG, PCAG, and LSD	Predose and 0.25, 0.5, 1, 1.5, 2, 2.5, 3, 4, 6, 8, 10, 12, and 24 hours postdose

Abbreviations: A = amphetamine; BG = Benzedrine Group; LSD = Lysergic Acid Diethylamide; MBG = Morphine-Benedrine Group; PCAG = Pentobarbital–Chlorpromazine–Alcohol Group; VAS = visual analog scale.

Windows for timed subjective measurements are presented in [Table 9-4](#).

**Table 9-4. Acceptable Windows for Timed Subjective Measurements**

Elapsed Time	Accepted Window
Predose (Day 1)	Within 60 minutes prior to study drug administration
Postdose	Within 5 minutes following pupillometry assessment

### 9.2.1 Visual Analogue Scales

All VAS will be scored on a 100-point scale, as shown in [Table 9-5](#), and will be administered at the timepoints specified in [Table 9-3](#). The VAS may be administered as bipolar or unipolar scales, as appropriate, and the choice is determined by the nature of the subjective effect being measured. Bipolar scales ask about the neutrality, the direction and the intensity of a subjective opinion, whereas unipolar scales only ask about the extremity or intensity of a subjective opinion. When VAS are administered as bipolar scales, a neutral point equal to 50 is embedded within the scale (e.g., Drug Liking, Overall Drug Liking, Take Drug Again, Drowsiness/Alertness VAS). The neutral point reflects a state whereby a subject is experiencing neither negative nor positive effects (e.g., neither dislike nor like the effects of the drug) and is

labeled with an anchor, such as “neither like nor dislike.” When VAS are administered as unipolar scales, anchors will be presented using text such as “Not at all” (score = 0) to “Extremely” (score = 100; e.g., Good, Bad, High, and Any Effects VAS). Unipolar scales do not include a neutral point but rather, a rating of “0” reflects the complete absence of a subjective effect while a rating of “100” reflects the maximum presence of a subjective effect (e.g., No Good Effects = 0, Extremely Good Effects = 100). Scales that refer specifically to drug (e.g., Drug Liking, Good Effects VAS, Bad Effects VAS, and Any Effects VAS) are not administered at predose.

**Table 9-5. Visual Analog Scale (VAS) Descriptions**

Scale Interpretation	Include Predose	Type of Scale	Description	Question Text	Response Anchors
Balance	No	Bipolar	Drug Liking	At this moment, my liking for this drug is	0: Strong disliking 50: Neither like nor dislike 100: Strong liking
Balance	No	Bipolar	Overall Drug Liking	Overall, my liking for this drug is	0: Definitely would not 50: Neither would nor would not 100: Definitely would
Balance	No	Bipolar	Take Drug Again	I would take this drug again	0: Definitely would not 50: Neither would nor would not 100: Definitely would
Positive	Yes	Unipolar	High	At this moment, I am feeling high	
Positive	No	Unipolar	Good Effects	At this moment, I feel good drug effects	
Negative	No	Unipolar	Bad Effects	At this moment, I feel bad drug effects	0: Not at all 100: Extremely
Other	No	Unipolar	Any Effects	At this moment, I feel any drug effect	
Other	Yes	Unipolar	Feeling Drunk	At this moment, I am feeling drunk	

Scale Interpretation	Include Predose	Type of Scale	Description	Question Text	Response Anchors
Other	Yes	Bipolar	Drowsiness/Alertness	At this moment, my mental state is	0: Very drowsy 50: Neither drowsy nor alert 100: Very alert
Other	Yes	Bipolar	Relaxation/Agitation	At this moment, my mental state is	0: Very relaxed 50: Neither relaxed nor agitated 100: Very agitated

### 9.2.2 Bowdle VAS

The Bowdle VAS consists of 13 items for which the subject is asked to rate his or her current feelings. An adapted computerized version of Bowdle VAS will be administered. The first 11 items are used to derive two composite scores reflecting internal and external perceptions. Each VAS will be administered using a unipolar format and scored from 0 to 100, with 0 reflecting “Not at all” and 100 reflecting “Extremely.” Lower individual and overall scores indicate fewer psychedelic effects.

The individual items of the questionnaire are listed below:

1. My body or body parts seemed to change their shape or position (BODY)
2. My surroundings seemed to change in size, depth, or shape (SURROUNDINGS)
3. The passing of time was altered (TIME)
4. I had feelings of unreality (REALITY)
5. It was difficult to control my thoughts (THOUGHTS)
6. The intensity of colors changed (COLORS)
7. The intensity of sound changed (SOUND)
8. I heard voices or sounds that were not real (VOICES)
9. I had the idea that events, objects, or other people had particular meaning that was specific for me (MEANING)
10. I had suspicious ideas or the belief that others were against me (SUSPICIOUS)
11. I felt anxious (ANXIOUS)
12. I felt high (HIGH)
13. I felt drowsy (DROWSY)

Responses to items 1, 2, 3, 5, 6, and 7 are summed to produce a “Subjective External Perceptions” composite score. Response to items 4, 8, 9, 10, and 11 are summed to produce a “Subjective Internal Perceptions” composite score. Items 12 and 13 will not be included as they are administered as part of the individual VAS items.

If a response to 1 of the items is missing, the associated composite score will not be calculated.

